Natural agents that can modulate the inflammation process have the potential to improve both cognitive and physical function through a number of biological pathways. Long term treatment of inflammatory disorders with NSAIDs (non-steroidal anti-inflammatory drugs) has the potential of serious side effects such as increased risk of gastrointestinal and cardiovascular disease, increased susceptibility to fracture, opportunistic infections, and peptic ulcers. Given the increasing use of anti-inflammatory agents among older individuals, studies are needed to examine their safety and efficacy.

Some natural compounds, such as curcumin, may have multiple physiological effects due to their anti-inflammatory and anti-oxidant properties. These findings are not unexpected given that curcumin has been found to activate a wide variety of targets, and produces broad, systemic effects that are very similar to caloric restriction, the only method to date that has been found to increase healthy lifespan in multiple species. Below we describe studies supporting the potential use of both of these compounds.

d. Curcumin. Curcumin is the bioactive polyphenolic extract of Turmeric, which has been used to treat inflammatory conditions in India for centuries. Findings over the past few decades indicate that curcumin has a broad range of biological properties, including anti-inflammatory and anti-oxidative properties, directly relevant to human health. In past clinical trials, doses ranging from 1000-2500 mg of curcumin per day have been found to be safe and well tolerated. The anti-inflammatory role of curcumin is supported by both in vitro and in vivo evidence. For example, curcumin has been found to inhibit TNF $\alpha$  -activated NF- $\kappa$  B signaling in adipocytes; thereby reducing cytokine expression. Curcumin's anti-inflammatory effects may be due in part to its ability to upregulate expression of peroxisome proliferator-activated receptor gamma (PPAR- $\gamma$ ). Small scale pilot trials have found supplementation with low doses of curcumin (i.e., 20 mg per day) was effective in reducing plasma fibrinogen levels and apolipoprotein B in patients with elevated cardiovascular risk factors. Most recently, supplementation with curcumin at a dose of 500 mg per day over an eight week period was found to significantly lower CRP levels in patients with rheumatoid arthritis.

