### Study Population

The RCT will include 24 moderately functioning, sedentary adults age 70 years or older with elevated levels of systemic inflammation but without overt disease conditions. We estimate that up to 324 potential participants will undergo screening procedures to identify 24 persons eligible for enrollment in the RCT.

Based on our previous studies, we anticipate that the average age of participants will be approximately 77.0 years, and that approximately 20% will be African Americans. In general, participants will have a relative low prevalence of comorbid diseases.

The key inclusion criteria are the following:

- (1) Age  $\geq 70$  years;
- (2) Mild to moderate physical impairment (Short Physical Performance Battery score  $\leq 10$ );
- (3) Sedentary lifestyle ( $< 120$  min per week of moderate intensity physical activity);
- (4) Chronic low-grade inflammation measured by IL-6  $> 2.5$  pg/ml. To minimize within person variability, IL-6 is the average of 2 measures taken 1-3 weeks apart at screening visits

See Table 1 for a complete list of eligibility criteria.

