### **Enrollment and Randomization**

24 eligible participants will be enrolled and randomized to allow for 6 participant failures or withdrawals

At the baseline visit, the Informed Consent document for the RCT will be reviewed with the potential participant and written consent obtained. Participants will undergo a battery of physical performance tests (400-meter walk; short physical performance battery, grip strength and endurance), formal tests of cognitive function, and a blood draw of about 60 ml (See Table 1). Quality of Life and pain will be assessed with the AM-PAC, the SF-36, and the Brief Pain Inventory (BPI). Self-report of physical activity and dietary fat intake will be obtained through brief questionnaires (RAPA and Block High Fat screen).

Participants will then be randomized to receive either curcumin (1000 mg/day; n = 15) or placebo (microcrystalline cellulose; n=15) for a three-month period. The study drug will be provided for the first month according to randomization.

Participants in both groups will be instructed to return to the research center every month for the duration of the three-month trial. At the monthly visits, compliance with the supplementation regimen for the previous month will be assessed by pill count and participants will be provided with another month's supply of study medication according to initial randomization. Participants will be queried about any adverse events they experienced since their previous visit and any medical history updates they may need to provide. Additionally, blood samples will be obtained (chemistry 15 panel and complete blood count) to ensure that no adverse changes have occurred since their previous visit.

To enhance retention and to ensure participant safety, participants will receive bi-weekly telephone calls throughout the intervention period to ascertain adverse events and express appreciation for participation.

Following the three month supplementation period (Month 3 visit), participants will complete a post-treatment assessment including the battery of physical performance tests (400-meter walk, short physical performance battery, grip strength and endurance); cognitive function tests; questionnaires for quality of life, pain symptoms, and physical activity; and a blood draw of approximately 60 ml (See Table 2).

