e. Pain Assessments. The Brief Pain Inventory (BPI) will be used to assess the presence and location of daily pains, as well as pain severity and pain-related interference. The BPI measures pain severity using a series of 0 (no pain) to 10 (worst possible pain) scales, which assess average pain, worst pain, and least pain in the past week, as well as current pain at the time of testing. There are seven BPI interference questions, each ranging from 0 (does not interfere) to 10 (completely interferes), assessing the extent to which pain has interfered over the past 24 hours with general activity, mood, walking ability, normal work, relations with other people, sleep, and enjoyment of life. This instrument has been validated for assessing outcomes in participants with non-cancer pain and has been used to quantify treatment outcomes.

f. Systemic Inflammatory biomarkers. Standard inflammatory biomarkers (i.e., IL-6, TNFa, and novel markers of inflammation) will be measured by ELISA at Baseline and the 3-month visit. All samples will be measured in duplicate and the average of the two measures will be used for data analyses.

g. Other measures

Dietary Fat (Block) questionnaire. Poor absorption of curcumin has been reported for various preparations, with enhanced absorption in high fat diets. This brief (13 item) "fat screen" identifies individuals with "high" fat intake, a potential confounder due to enhanced curcumin absorption.

Self-reported physical activity. The Rapid Assessment of Physical Activity (RAPA) is a 9-item questionnaire developed to assess strength, flexibility, and level and intensity of physical activity among older adults.

Safety. As a safety check to ensure no adverse biological changes have occurred, the following measures will be completed at screening, baseline, and each monthly visit:

- Study Coordinator will review any changes in medication, ED visits or hospitalizations, or side effects since previous visit with the participant
- At monthly visits, 30 cc of blood will be drawn and analyzed for a CHEM-15 metabolic profile (Albumin, Albumin/Globulin Ratio (calculated), Alkaline Phosphatase, ALT, AST,

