## **Statistical Analyses**

Sample size estimates for pilot studies are inherently difficult because by intent, a pilot study is meant to include a smaller sample than a fully powered study. The enrollment sample of 15 participants in the intervention group and 15 participants in the placebo group (allowing for at least 12 evaluable participants in each group after the expected 20% loss due to attrition) is intended to provide sufficient data to indicate feasibility of a larger study and to provide descriptive estimates of effects. Additionally, it will provide for nominal estimation (using a 95% confidence interval) of the mean changes in the inflammatory marker, IL-6, the primary outcome of this pilot.

Feasibility and acceptability of the proposed intervention in older adults will be evaluated by process variables including number of participants completing the study; medication compliance, number and severity of adverse events, and changes in Quality of Life attributable to study participation.

Efficacy will be assessed as effects of the intervention on functional performance (physical and cognitive measures; pain perception, and inflammatory processes (Specific Aims). The following outcomes will be evaluated: physical function (walking speed, muscle fatigue); cognitive function (attention, executive, and memory function); pain (self-report); and systemic inflammation (IL-6, CRP, TNF $\alpha$ , and novel markers)

For each outcome, we will take the value of that outcome after the 3-month supplementation period minus the value at baseline for each participant. Summary statistics and 95% confidence intervals will be provided for within group changes as well as between group differences.

Effect size of intervention on key outcomes for sample size calculations in the planning of a larger RCT. Based on a sample size of 15 per group and 20% attrition, we have 80% power to detect a between group difference of effect size 1.2. Specifically, if we use the root mean squared error from LIFE-P (adjusted for baseline log(IL-6) and treatment) of 0.52 for log(IL-6), then we can detect a mean difference of 0.62 (on the log scale) or equivalently the difference between 4.20 and 2.26 pg/ml (or a 46% difference). And for selection based on walking speed change, we used a within group standard deviation of 0.25, which leads to a detectable mean difference of 0.3 m/s.

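### The planned between-arm IL-6 comparison is an unadjusted change score, but the 80% power rests on a baseline-adjusted SD; a pre-treatment covariate using the screening IL-6 values would close the gap without new samples

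*Combined protocol and SAP*

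**What the plan says.** Statistical Analyses names the "mean changes in the inflammatory marker, IL-6, the primary outcome of this pilot". The analysis rule for all outcomes is: "For each outcome, we will take the value of that outcome after the 3-month supplementation period minus the value at baseline for each participant". No covariate is mentioned. Results are to be reported descriptively with 95% intervals, for each group and for the difference between groups.

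The power statement in the same section uses 15 per arm, 20% attrition and an effect size of 1.2. It takes a root mean squared error of 0.52 for log(IL-6) from LIFE-P, described there as adjusted for baseline log(IL-6) and treatment. That gives a detectable log difference of 0.62, or 46%.

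For entry, Study Population says that "IL-6 is the average of 2 measures taken 1-3 weeks apart at screening visits", with the stated aim of reducing within-person variability. For the outcome, section f of Outcome Measures (Systemic Inflammatory biomarkers) says that the markers "will be measured by ELISA at Baseline and the 3-month visit". Each sample is assayed twice, and the mean of the two results is analysed. The IL-6 row of Table 2 is marked at Screening visit 1 and the 3-Month visit, and not at Baseline. The monthly blood is assigned to a chemistry panel and blood count for safety (Enrollment and Randomization; Safety, under Outcome Measures).

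**The concern.** The plan recognises that a single IL-6 draw is noisy and averages two draws to decide who enters. It does not say that this information is carried into the primary comparison. Duplicate wells from one sample reduce assay error and leave day-to-day variation within a person untouched.

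An unadjusted change score carries the full noise of the baseline draw as well as that of the Month 3 draw. Baseline adjustment removes part of it, and the 0.52 already has that benefit built in. The plan therefore quotes the precision of one analysis and specifies another. With about 12 evaluable participants per arm, and with interval estimates and an effect size for a later trial as stated purposes, the difference matters.

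**Working it through.** **Inputs from Statistical Analyses.** Adjusted SD 0.52; effect size 1.2; log difference 0.62; 12 evaluable per arm. Two-sided alpha of 0.05 is assumed from the 95% interval.

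**The plan's own figure.** 15 × (1 − 0.20) = 12 per arm. Noncentral t power at effect size 1.2 is 80.2%. 1.2 × 0.52 = 0.62, and 4.20 × exp(−0.62) = 2.26, a 46% difference. The figure reproduces. At 0.62/0.52 exactly, power is 79.7%.

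**Assumptions not in the documents.** The 0.52 comes from one draw before and one after treatment. All draws have the same variance s² and the same pairwise correlation ρ, shown for 0.3 to 0.7. The change is analysed on the log scale, as in the power statement; the analysis rule does not say so.

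**Formulas.**
- Single-draw variance: s² = 0.52² / (1 − ρ²)
- Change score, one baseline draw: variance = 2s²(1 − ρ)
- ANCOVA on the mean of k pre-treatment draws: variance = s²[1 − ρ² / (ρ + (1 − ρ)/k)]

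**Worked case, ρ = 0.5.** s² = 0.2704/0.75 = 0.3605.
- Change score: √(0.3605 × 2 × 0.5) = 0.600
- ANCOVA, k = 2: √(0.3605 × (1 − 0.25/0.75)) = 0.490
- ANCOVA, k = 3: √(0.3605 × (1 − 0.25/0.667)) = 0.475

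**SD, and power for 0.62 with 12 per arm**

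| Analysis | ρ = 0.3 | ρ = 0.5 | ρ = 0.7 |
|---|---|---|---|
| Change score, one baseline draw | 0.645, 61% | 0.600, 68% | 0.564, 73% |
| ANCOVA, one baseline draw (the 0.52) | 0.520, 80% | 0.520, 80% | 0.520, 80% |
| ANCOVA, two screening draws | 0.506, 82% | 0.490, 84% | 0.474, 86% |
| ANCOVA, three pre-treatment draws | 0.497, 83% | 0.475, 86% | 0.453, 89% |

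These powers use 22 degrees of freedom. Using 21 for the ANCOVA rows lowers them by about 0.2 points.

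**Precision.** The detectable difference at 80% power is 1.197 × SD. It is 0.77 to 0.68 (54% to 49%) for the change score and 0.59 to 0.54 (45% to 42%) for three-draw ANCOVA. The 95% interval half-width, 2.074 × SD × √(2/12), falls from 0.55–0.48 to 0.42–0.38.

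**If the screening mean were the baseline of the change score.** Variance is s²(1 − ρ)(1 + 1/2), so SD is 0.56 to 0.49 and power 74% to 84%. Two-draw ANCOVA still does better at every ρ shown.

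**A Month 2 draw averaged with Month 3, change score, one baseline draw.** The variance factor goes from (1 + 1) to (1 + 1/2), a 25% cut at any ρ. Power becomes 74% to 84% if the true effect is the same at both visits. If the Month 2 effect is a fraction f of the Month 3 effect, the averaged effect is (1 + f)/2 of it. Break-even is therefore f = 2√0.75 − 1 = 0.73. At f = 0.75, power is 62%, 69% and 74%, so there is almost no gain. At f = 0.50 it is 50%, 55% and 61%, below the current plan.

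**The case against.** The best defence is that this is a pilot for feasibility and descriptive estimates. A change score with one endpoint draw is a legitimate choice and the power arithmetic is correct. That stands: the 80% is no calculation error, and nothing here biases the comparison between arms. What remains is that the SD and the planned analysis do not match, and that better precision is available from values already measured.

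It may also be said that the averaged screening value could be the intended baseline. The documents do not rule this out. Table 2 has no IL-6 mark at Baseline, while the biomarker section says that it is measured there. The loss is then smaller (74% to 84% power), but the ambiguity itself needs settling.

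The correlation is assumed. Draws closer in time may resemble each other more than draws three months apart, so the equal-correlation model is a simplification.

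A reader might go further and infer that blood lies unused at Month 2, and that averaging it with Month 3 would lift power from 80% to above 90%. The documents do not support this:
- The Month 2 blood is used for safety laboratory tests. It is only not assayed for IL-6, and no stored plasma is described.
- Gains of that size belong to a baseline-adjusted analysis that the plan does not specify, and they need an equal effect at both visits.
- The Background's evidence at eight weeks ("over an eight week period was found to significantly lower CRP levels") concerns a different marker, patients with rheumatoid arthritis and 500 mg per day. It gives no Month 2 to Month 3 ratio for IL-6 here.
- A Month 2–3 mean is a different target from the three-month effect. Making it primary is a trade-off.

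**Conclusion.** The point holds as an efficiency weakness, together with a mismatch between the power statement and the analysis. Under the stated assumptions, the planned change score from one baseline draw has about 61% to 73% power for the 0.62 difference, against the 80% quoted. ANCOVA on all pre-treatment values gives about 83% to 89% with three values and 82% to 86% with the two screening values. That the two analyses differ follows from the documents. The size of the gap rests on the assumed correlation and on 0.52 being a single-draw SD.

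The conflict between 24 and 30 randomised does not alter the point, but a smaller trial would make precision matter more. The case for a Month 2 assay is weaker, because it depends on an effect ratio that the documents do not give.

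**What to change.** 1. In Statistical Analyses, define the between-arm IL-6 comparison as ANCOVA of Month 3 log(IL-6) on treatment. The covariate is the mean of all available pre-treatment log(IL-6) values: the two screening values, plus the Baseline value if assayed. Report the adjusted difference with its 95% interval.
2. Do not use the screening mean as the starting point for within-group change. Participants are selected for a high screening mean, so later values would tend to fall by regression to the mean without any treatment effect. Randomisation balances this between arms, but nothing balances it within an arm. Within-group change should start from the Baseline-visit value.
3. Reconcile the biomarker section with Table 2 on whether IL-6 is assayed at Baseline, and state which values form the baseline.
4. Optional: set aside a plasma aliquot from the scheduled Month 2 draw and report the Month 2–3 mean log(IL-6) as a supportive analysis, keeping Month 3 primary.

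Items 1 to 3 cost a few sentences, and one table mark if Baseline is confirmed. They need no new visit or draw, and the three-month target is unchanged. Item 4 costs 24 to 30 more samples in duplicate (48 to 60 wells), plus handling and storage.

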### Specific Aims:

Specific Aim 1 - To examine the effects of dietary supplementation with curcumin on changes in physical function (walking speed, muscle fatigue, and grip strength) and in

self-reported physical activity

*Hypothesis 1 – Dietary supplementation with curcumin will maintain or improve walking speed, muscle fatigue, strength, and physical activity compared to controls.*

*Specific Aim 2 – To examine the effects of dietary supplementation with curcumin on cognitive performance (attention, memory), and pain symptoms.*

*Hypothesis 2 - Dietary supplementation with curcumin will maintain or improve attention and memory and reduce pain symptoms.*

*Specific Aim 3 – To examine the effects of dietary supplementation with curcumin on markers of systemic inflammation*

*Hypothesis 3 - Dietary supplementation with curcumin will decrease levels of IL-6 and of other systemic and cellular biomarkers of inflammation*

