Approximately 3-4 weeks after the Month 3 visit (at Week 15 – 16), participants will receive a final telephone call to ascertain any late adverse events, discuss any abnormalities from the final safety lab results, and express appreciation for participation.

Table 2. Study Visit Schedule Visit Type	Phone screen (pre-screening)	Screening visit 1		Baseline visit	Week 2	1-Month Visit	Week 6	2-Month Visit	Week 10	3-Month visit	Week 15-16
	Basic eligibility screening	X	X								
Informed Consent (Screening)		X									
Health review and physical examination (including BP, pulse, weight, height, waist circumference)		X									
Medical History and Concomitant Medication		X									
Update Medical History and Concomitant Medication Info				X	X	X	X	X	X	X	
BP, pulse, height and weight, waist circumference		X		X	X	X	X	X	X	X	
MMSE, CES-D		X									
Physical Activity Questionnaire (RAPA)				X						X	
SPPB (including 4 m walk test)		X		X						X	
Phlebotomy		X		X	X	X	X	X	X	X	
IL-6		X								X	
Additional exploratory inflammatory markers (TBD)				X						X	
CBC and Comprehensive Metabolic Panel (CMP) (Safety blood tests)		X		X	X	X	X	X	X	X	
Informed Consent (Main Study), enrollment, and randomization				X							
400 m walk test				X						X	
Isokinetic dynamometry of knee flexors and extensors				X						X	
Isometric hand grip strength				X						X	
Cognitive Function Tests (NIH Toolbox)				X						X	
Quality of Life (AM-PAC, SF-36)				X						X	
Brief Pain Inventory				X						X	
Dietary Fat questionnaire (Block)				X							
Dispense study drug				X	X	X	X	X	X	X	
Scheduled phone call					X	X	X	X	X	X	X
Assess compliance, query adverse effects and events						X	X	X	X	X	X

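### For the functional, cognitive and pain outcomes the plan uses baseline only by subtraction; a baseline-adjusted between-group estimate would be a nearly free, optional improvement

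*Combined protocol and SAP*

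**What the plan says.** Section 6, Statistical Analyses, defines the analysis variable for every outcome: "For each outcome, we will take the value of that outcome after the 3-month supplementation period minus the value at baseline for each participant". The comparison is then described in one sentence: "Summary statistics and 95% confidence intervals will be provided for within group changes as well as between group differences". No regression model, test or baseline covariate is named.

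The outcomes are listed in the same section: "The following outcomes will be evaluated: physical function (walking speed, muscle fatigue); cognitive function (attention, executive, and memory function); pain (self-report"), followed by systemic inflammation. Self-reported physical activity is not on that list, but it is part of Hypothesis 1 in Specific Aims: "Dietary supplementation with curcumin will maintain or improve walking speed, muscle fatigue, strength, and physical activity compared to controls". The change-score rule reaches it only because the rule is written for each outcome.

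The baselines exist. Enrollment and Randomization, with Table 2, places the walk tests, "Cognitive Function Tests (NIH Toolbox"), the Brief Pain Inventory and the RAPA at both the baseline and the 3-month visit.

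Statistical Analyses plans for 15 per arm and, with one in five expected to drop out, counts on no fewer than 12 per arm for analysis. Enrollment and Randomization instead speaks of 24 randomized with room for six losses, and then gives 15 per arm a few lines later. For walking speed, "we used a within group standard deviation of 0.25, which leads to a detectable mean difference of 0.3 m/s". For log(IL-6), the same paragraph uses an error SD of 0.52 that is adjusted for baseline.

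**The concern.** A change score treats the slope of the Month 3 value on baseline as exactly 1. With equal SDs at the two visits the slope is r, the correlation between them. When r is below 1, subtraction over-corrects: the arm that happens to start higher tends to show the smaller gain. This has two consequences. The interval is wider than it need be for small or moderate r, and the point estimate moves with whatever imbalance randomization leaves.

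This matters because of what the pilot is for. Section 5 lists effect sizes for sizing future trials as an overall objective, and the Statistical Analyses section describes the sample as a source of descriptive estimates. A later planner will take this one trial's point estimates at face value. With small arms, and no stratification described, sizeable baseline differences will be common. The plan's own power statement for IL-6 already relies on a baseline-adjusted error, so the idea is not foreign to it.

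**Working it through.** **Inputs.** From Statistical Analyses: 12 evaluable per arm, 80% power, standardized difference 1.2, walking-speed SD 0.25. Assumed: two-sided 5% level (in line with the 95% intervals), equal SDs at baseline and Month 3, a common linear slope, and r from 0.3 to 0.95. The documents do not give r.

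**The plan's own figure.** A two-sample t-test with 12 per arm (22 df, noncentral t) has 80.2% power at 1.2 SD; the detectable difference at 80% is 1.197 SD. For walking speed, 1.2 × 0.25 = 0.30 m/s, or 1.197 × 0.25 = 0.299. The stated figure reproduces.

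**Size of chance imbalance.** The standard error of a baseline difference is sqrt(2/12) = 0.41 SD. The chance that it exceeds 0.5 SD in either direction is 2 × [1 − Φ(0.5/0.408)] = 22%.

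**Effect on the estimate.** Given an imbalance, the change-score contrast shifts by (1 − r) × imbalance, against the arm that starts higher. For 0.5 SD that is 0.5 × 0.5 = 0.25 SD at r = 0.5, and 0.3 × 0.5 = 0.15 SD at r = 0.7. Across repeated trials the correlation between estimate and imbalance is −sqrt((1 − r)/2): −0.50 at r = 0.5, −0.32 at 0.8, −0.22 at 0.9. A simulation of 20,000 trials per value of r gave −0.49, −0.32 and −0.22, and about 0 after adjustment. Coverage was 95% for both methods.

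**Effect on interval width.** Adjusted width divided by change-score width is

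sqrt[ (1 + r)/2 × (1 + 1/(N − 4)) ] × t(N − 3)/t(N − 2).

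With N = 24 the middle factor is 1.05, and the ratio of t quantiles (21 against 22 df) is about 1.003. The last column applies only if 0.25 m/s is the SD of change.

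| r | Width ratio | Half-width, m/s (0.212 unadjusted) |
|---|---|---|
| 0.3 | 0.83 | 0.175 |
| 0.5 | 0.89 | 0.188 |
| 0.7 | 0.95 | 0.201 |
| 0.8 | 0.97 | 0.206 |
| 0.9 | 1.00 | 0.212 |
| 0.95 | 1.01 | 0.215 |

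The unadjusted half-width is 2.074 × 0.25 × sqrt(2/12) = 0.212.

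**Walking-speed detectable difference.** If 0.25 is the SD of change, 0.299 becomes 0.299 × 0.89 = 0.27 at r = 0.5, 0.299 × 0.947 = 0.28 at r = 0.7, and stays at 0.30 at r = 0.9. If 0.25 is the SD of speed itself, the SD of change is 0.25 × sqrt(2(1 − r)): 0.19 at r = 0.7 and 0.16 at r = 0.8. The unadjusted detectable difference would then be about 0.23 or 0.19 m/s. The meaning of 0.25 therefore matters more than the choice of model.

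**The other enrolment count.** With 24 randomized and six lost, 18 remain, or 9 per arm. The imbalance standard error is sqrt(2/9) = 0.47 SD, and the chance of exceeding 0.5 SD is about 29%. The width formula with N = 18 (factor 1 + 1/14, 15 against 16 df) gives about 10% narrowing at r = 0.5, 4% at r = 0.7, and 1% widening at r = 0.9. Power at 1.2 SD is 66.7%.

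**The case against.** Three stronger readings are tempting, and the documents do not support them.

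- *That the baselines go unused.* They are used, by subtraction. Under equal SDs, once r exceeds 0.5 this already beats comparing Month 3 values alone. If 0.25 is the SD of speed and r = 0.8, the half-width is 0.134 m/s for change against 0.212 for Month 3 values. What is missing is an estimated slope.
- *That the planned comparison is biased or its intervals wrong.* Under randomization the change-score difference is unbiased, and its interval already contains the variability due to imbalance. The shift above describes accuracy given the imbalance that occurs, not bias.
- *That the plan forbids adjustment.* It defines the variable and is silent on the model. A model of change on arm and baseline gives the same treatment estimate as the Month 3 model, so the definition does not rule adjustment out. But no such model is specified, and silence leaves the choice open until the data are seen.

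The defence also notes that the gain hangs on an unknown r. The only repeatability figure in the documents is an ICC of 0.97 for strength testing (Physical Function Measures), where adjustment would bring nothing. These are also non-primary outcomes in a descriptive pilot, and Aim 1 is itself framed in terms of change. All of this stands, and it keeps the point an optional improvement. It does not remove the dependence on chance imbalance, which matters to anyone planning from a single small trial.

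**Conclusion.** The point holds in a limited form. The plan specifies no baseline-adjusted between-group estimate for the functional, cognitive and pain outcomes, although their baselines are collected. The planned comparison is valid but not the most efficient available, and its estimates remain tied to chance imbalance. At 12 per arm, adjustment narrows the interval by about 11% at r = 0.5, 5% at 0.7 and nothing at 0.9, with a loss of about 1% at 0.95. These figures rest on equal SDs, a common linear slope and an assumed r. The figure of 12 per arm holds only for the version with 15 randomized per arm. This is a free improvement, not the repair of an invalid analysis.

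**What to change.** In Statistical Analyses:

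- State that the between-group difference for each functional, cognitive and pain outcome is estimated from a linear model of the Month 3 value on arm and that outcome's own baseline value, with a 95% interval. Keep raw changes within and between groups as descriptive summaries.
- Include self-reported physical activity, which is an Aim 1 outcome, and add it to the outcome list.
- Say whether the walking-speed SD of 0.25 refers to change or to speed, and restate the detectable difference to match that meaning and the chosen model. If r is assumed, give its value and source.
- Reconcile the enrolment counts (24 with six losses against 15 per arm), and state the evaluable number per arm that follows.

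The cost is a few sentences and one degree of freedom per model. No new data, visits or participants are needed. At 12 per arm the worst case in the range examined is an interval about 1% wider, at r = 0.95.
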